9.1.5 Adverse Event Reporting

Add adverse events will be reported to the University of Virginia IRB-HSR according to guidelines. Any unanticipated problem or serious and unexpected adverse events will require re-evaluation of the risk of the study. [name] will be the person to whom all unanticipated problems or serious and unexpected adverse events, whether psychological or medical, are initially reported. [name] is a licensed clinical psychologist who can evaluate whether the events are SAEs or AEs. [name] will be responsible for ensuring that all unanticipated problems or serious and unexpected adverse events are reported within 48 hours to the IRB and NCATS. Adverse events will be monitored carefully and any necessary steps will be taken to maintain participant safety. Any change to the procedures will be forwarded to the IRB for approval. The NCATS Project Officer will receive an annual report summarizing all adverse events.

9.2 Protocol Deviation

9.2.1 Definition of Protocol Deviation

A protocol deviation is any noncompliance with the clinical trial protocol, International Conference on Harmonisation Good Clinical Practice (ICH GCP), or Manual of Procedures (MOP) requirements. The noncompliance may be either on the part of the participant, the investigator, or the study site staff. As a result of deviations, corrective actions are to be developed by the site and implemented promptly.

These practices are consistent with ICH GCP:

- 4.5 Compliance with Protocol, sections 4.5.1, 4.5.2, and 4.5.3
- 5.1 Quality Assurance and Quality Control, section 5.1.1
- 5.20 Noncompliance, sections 5.20.1, and 5.20.2.

9.2.2 Reporting of a Protocol Deviation

It is the responsibility of the site investigator to use continuous vigilance to identify and report deviations. All deviations must be addressed in study source documents, reported to [name].

9.3 Participant Withdrawals/Dropouts Prior to Study Completion

Participants who withdraw consent and those dropping out of the study secondary to an AE will be reported to the IRB of record according to IRB guidelines.

10 STATISTICAL CONSIDERATIONS

10.1 Statistical Hypotheses

Primary hypothesis: caregivers' engagement with SHUTi (i.e., being a non-user vs. incomplete user vs. complete user) will be associated with their caregiving-related user characteristics (i.e., caregiving strain, self-efficacy, and guilt) and environment characteristics (i.e., proximity to care recipient; care recipient functional, cognitive, and behavioral status; caregiving tasks).

Secondary hypothesis: the effects of SHUTi on cognitive mechanisms of change targeted by SHUTi (i.e., more adaptive sleep beliefs, internalized sleep locus of control) will differ by caregiving-related user characteristics (i.e., caregiving strain, self-efficacy, and guilt) and environment characteristics (i.e., proximity to care recipient; care recipient functional, cognitive, and behavioral status; caregiving tasks).

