3 OBJECTIVES AND ENDPOINTS

Objectives	Endpoints
Primary	
To test the association of SHUTi engagement with caregiving context.	Level of engagement: non-users (i.e., completed no Cores), incomplete users (i.e., completed 1 to 3 Cores), and complete users (i.e., completed 4 to 6 Cores)
Secondary	
To describe caregivers' barriers and motivations for SHUTi engagement	
 • Open-ended feedback about SHUTi • SHUTi utility and barriers: Internet Intervention Utility, Evaluation, and Adherence questionnaires
To test the association of SHUTi efficacy on known cognitive mechanisms with caregiving context.	
Cognitive mechanisms of change targeted by SHUTi
 
 • Sleep beliefs: Dysfunctional Beliefs and Attitudes about Sleep scale • Sleep control: Sleep Locus of Control Scale

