4 STUDY DESIGN

4.1 Overall Design

This study comprises a single-arm (nonrandomized) clinical trial with quantitative and qualitative data collection.

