Caregiving self-efficacy	Pearlin Stress Scale – Caregiving Competence subscale	✓	
Caregiving guilt	Caregiver Guilt Questionnaire – Guilt about doing wrong by the care recipient, guilt about not rising to the occasion as a caregiver, guilt about self-care subscales	✓	
Predictors: Caregiving-related environment characteristics			
Proximity to CR	Whether bedpartner, live together but not bedpartner, other situation	✓	
CR functional status	Modified Barthel Activities of Daily Living [ADL] Index	✓	
CR cognitive status	Pearlin Stress Scale – Cognitive Status subscale	✓	
CR problem behavior	Pearlin Stress Scale – Problematic Behavior subscale (includes night-time problems)	✓	
Caregiving tasks	Involvement in supporting ADL, Instrumental ADL, and nursing tasks	✓	
Changes in caregiving	Single item question (with follow-up open-ended response) if caregiving situation has significantly changed during study		✓
Aim 1 Outcomes: SHUTi engagement (Core completion recorded through SHUTi online platform)			
Core completion	Non-user (no Cores completed); Incomplete user (1-3 Cores); Complete user (4-6 Cores)	Through SHUTi	
Open-ended feedback	Free-response survey items – separate surveys for non-users and users		✓
SHUTi utility and barriers	Internet Intervention Utility, Evaluation, and Adherence Questionnaires – select items		✓*
Aim 2 Outcomes: SHUTi efficacy on known cognitive mechanisms			
Sleep beliefs	Dysfunctional Beliefs and Attitudes About Sleep	✓	✓*
Sleep control	Sleep Locus of Control Scale	✓	✓*
Exploratory: Preliminary Efficacy			
Insomnia severity	Insomnia severity index	✓	✓
Sleep diary metrics	10 days of sleep diaries in 14 day period	✓	✓*

*SHUTi users only

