10.3.2 Analysis of the Secondary Endpoint(s)

To describe caregivers' barriers and motivations for SHUTi engagement, qualitative coding of users' open-ended survey responses from post-assessment will be conducted via Dedoose software. Data will be coded using two methods: First, using an a priori codebook to tag data according to whether it is: (a) specific to SHUTi; (b) specific to CBT-I, but not exclusively SHUTi; or (c) specific to digital health interventions, but not exclusively SHUTi. This will facilitate examination of the extent to which caregiver-specific tailoring recommendations are specific to SHUTi versus generalizable to other evidence-based psychosocial digital health interventions. Responses will next be coded inductively using thematic text analysis⁸⁹⁻⁹¹ to identify themes related to caregivers' barriers to and motivations for SHUTi uptake and usage, as well as how caregiver-specific tailoring may affect each of those constructs. Each response will be coded by two independent coders with discrepancies resolved by consensus. The coding team will iteratively determine a set of codes; identify, review and name themes; and synthesize data into final actionable recommendations for tailoring SHUTi and other digital health interventions for caregivers.

Findings and resultant recommendations will be returned to caregivers for synthesized member checking⁹²:

- (1) A concise report of results will be sent to caregivers;
- (2) Caregivers will review the report and comment on how results compare/contrast with their experiences and needs; and
- (3) Caregivers' returned responses will be coded to ascertain level of resonance between caregivers' reported experiences and the researchers' original results. Findings and recommendations will be revised according to synthesized member checking results.

To test whether the effects of SHUTi on cognitive mechanisms (i.e., more adaptive sleep beliefs, internalized sleep locus of control) are associated with caregiving context, a continuous regression model will be computed for each user and environment characteristic on each cognitive mechanism assessed at post, controlling for pre-assessment level of the mechanism.⁹³ Caregivers who are SHUTi users (incomplete and complete; not non-users) will be included, and models will control for level of SHUTi engagement and pre-specified covariates, with significance set at $p < .05$.

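### The secondary hypothesis is about differences in SHUTi's effect, but the single-arm model estimates only the association of a characteristic with post scores, prognosis included

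*Combined protocol and SAP*

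**What the plan says.** - **Design.** Section 4.1: "This study comprises a single-arm (nonrandomized) clinical trial with quantitative and qualitative data collection". The Synopsis (1.1) defends the single arm as a mechanism-focused pilot meant to establish plausibility before larger efficacy testing.
- **Hypothesis.** Section 10.1 predicts that "the effects of SHUTi on cognitive mechanisms of change targeted by SHUTi" will vary with caregiving strain, self-efficacy, guilt and the listed environment characteristics.
- **Objective.** Section 3, repeated in the Synopsis: "To test the association of SHUTi efficacy on known cognitive mechanisms with caregiving context".
- **Model.** Section 10.3.2: "a continuous regression model will be computed for each user and environment characteristic on each cognitive mechanism assessed at post, controlling for pre-assessment level".
- **Analysis set and adjustment.** Section 10.3.2: "Caregivers who are SHUTi users (incomplete and complete; not non-users) will be included, and models will control for level of SHUTi engagement", together with the pre-specified covariates.
- **Data collected.** In the section 8.1 survey table, the post measurements of sleep beliefs and sleep control carry a footnote: "SHUTi users only".
- **Power.** Section 10.2 states 80% power with 78 users for the effect of a characteristic on the mechanisms at post, at R² = .04.

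**The concern.** A statement that an intervention's effect differs between kinds of people is a statement of effect modification. To test it, one must know how the characteristic relates to later scores with the intervention and without it. This trial observes only the first. If the sleep beliefs of high-strain caregivers would change differently over the nine-week access period anyway, the planned regression returns a non-zero coefficient even when SHUTi does exactly the same for everyone.

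This matters because section 2.1 says the findings will steer the next research on tailoring and testing SHUTi for caregivers. A prognostic marker read as a sign of weaker SHUTi efficacy would point that work at the wrong target. The reverse error is also possible: prognosis and modification of opposite sign can cancel and hide a real moderator.

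**Working it through.** **1. What the coefficient contains.** Let X be a characteristic and T indicate exposure to SHUTi. A model that allows both prognosis and modification is

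post = α + ρ·pre + βP·X + T·(δ + βM·X) + error,

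where βP is the association of X with the later score without SHUTi, and βM is the change in SHUTi's effect per unit of X. Everyone analysed has T = 1, so the model reduces to

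post = (α + δ) + ρ·pre + (βP + βM)·X + error.

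The planned test concerns βP + βM; the hypothesis in 10.1 concerns βM. Adjusting for the pre score and covariates reduces confounding of X but supplies no data at T = 0. Non-users cannot provide even an informal comparison, because their post mechanism scores are not collected (8.1). The model also adjusts for engagement, a post-baseline variable that the primary hypothesis expects to depend on the same characteristics. That clouds a causal reading further.

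**2. The plan's own figure.** Inputs: n = 78, 80% power, α = .05 (10.2). Assumed: two-sided test, complete post data. Predictors: pre score, engagement, age, income, health literacy, mental and physical health-related quality of life (seven), plus the characteristic, eight in all. Residual df = 78 − 8 − 1 = 69. Method: noncentral F with 1 and 69 df and noncentrality λ = n·f².

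- 80% power requires f² = 0.1035, that is, partial R² = 0.1035/1.1035 = 0.094.
- R² = .04 read as a partial R² gives 43% power.
- R² = .04 read as an increment needs .04/(1 − R²base − .04) = 0.1035, so the other predictors must already explain R²base ≈ 57%.

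Section 10.2 states neither the type of R² nor the base, so the figure can be neither confirmed nor refuted. The present point does not depend on it. What matters here is that the powered quantity is an effect on the post level, not a difference in SHUTi's effect.

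**3. How often pure prognosis would reach significance.** Set βM = 0 and assume a prognostic partial R². The documents give no value, so a range is shown. λ = 78·R²/(1 − R²); critical F(1, 69) = 3.98.

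| Assumed prognostic partial R² | λ | Significant |
|---|---|---|
| 0 | 0 | 5% |
| .01 | 0.79 | 14% |
| .02 | 1.59 | 24% |
| .04 | 3.25 | 43% |
| .10 | 8.67 | 83% |

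These are the ordinary power values of the planned test, evaluated where the signal is prognosis alone.

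**4. Simulation check.** Post on pre and X, n = 78, 4,000 runs, assumed pre–post correlation 0.6, component size equivalent to partial R² = .093.

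- Prognosis only: significant in 78% of runs.
- Modification only, same size: 79%.
- Equal and opposite prognosis and modification: 5%.

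The test responds alike to the first two cases and is blind to the third. For contrast, a treatment-by-characteristic test in a 1:1 two-arm version with 78 participants rejects in 5% of runs under pure prognosis, as it should. It would need about 312 participants (4 × 78) for 80% power against modification of that size.

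**The case against.** **The single arm is justified.** The Synopsis gives a reasoned case for a plausibility pilot over an underpowered randomised trial. That stands as a reason for the design. It does not make effect modification estimable.

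**SHUTi is held constant.** Section 2.2.1 argues that this isolates the user and environment effects. It removes variation in the intervention, but the characteristic's association without SHUTi is still unobserved.

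**Much of the wording is already associational.** This stands in part. The objective in section 3 is framed as an association, 10.3.2 asks whether effects are associated with context, and 10.2 powers an effect at post. However, the thing said to be associated is still SHUTi's efficacy or effects, and 10.1 says outright that the effects will differ.

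**The error rates rest on an undocumented assumption.** This stands in full. A reader might infer that the trial would wrongly declare a moderator 43% to 83% of the time. The documents do not support that: they give no prognostic effect on sleep beliefs or sleep locus of control. The values .04 and .10 appear in 10.2 only in connection with the effect the trial hopes to detect, and smaller prognostic effects give much lower rates.

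**The consequence should not be overstated.** This also stands. A reader might infer that a significant coefficient will be reported as SHUTi working less well in some caregivers, or will set the tailoring recommendations. No section says the first. On the second, 10.3.2 derives its actionable tailoring recommendations from qualitative coding and member checking. Treating a positive result as a lead for later testing is close to the pilot's stated purpose.

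**Conclusion.** The concern holds as a mismatch between claim and estimand. The hypothesis in 10.1 concerns a difference in SHUTi's effect. The analysis in 10.3.2 estimates prognosis plus modification in treated users, and only that sum can be estimated. No section limits the conclusion accordingly. This follows from the design and needs no numerical assumption.

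The size of the risk is unknown. Under the assumptions in the working (78 users with complete post data, two-sided .05, an assumed prognostic effect), pure prognosis would be significant anywhere from 5% of trials at partial R² = 0 to 83% at .10. The table illustrates this and does not estimate what this trial will do.

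A reader might also conclude that the trial needs a control arm. That does not follow: the association among users is a legitimate pilot question and the planned model addresses it. The point is worth acting on because it changes what the secondary analysis may conclude, but it concerns a secondary hypothesis in a declared pilot.

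**What to change.** In sections 1.1, 3, 10.1 and 10.3.2:

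1. Restate the secondary hypothesis and objective along these lines: *among SHUTi users, post-intervention mechanism scores, given baseline, are associated with caregiving characteristics.*
2. Add to 10.3.2 that the analysis does not test whether SHUTi's effect differs between caregivers, because the coefficient combines prognosis with any effect modification.
3. State that a positive result identifies a candidate moderator for a later controlled trial, and that a null result does not exclude one.

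The cost is a few sentences and a less favourable claim. No new data, participants or models are needed, and the section 10.2 power statement already refers to an effect at post.

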10.2 Sample Size Determination

We will enroll up to about 130 high-intensity caregivers with insomnia into this single-arm (nonrandomized) trial. The minimum sample size to achieve is 100. Based on completion rates from [name] (University of Pittsburgh site PI) untailored Internet depression management program (non-users = 35%; incomplete = 40%; complete = 25%) and averages across SHUTi trials (non-users = 10%; incomplete = 25%; complete = 65%), we estimate that the sample in the proposed trial will break down as follows: 22% non-users, 33% incomplete users, 45% complete users. Assuming these response rates, the minimally detectable proportional odds (minOR) analyses at power = 80% with $\alpha = .05$ would be a moderate effect size⁹⁴ (minOR= 2.9) for a sample size of N = 100 based on rate of dichotomized predictor exposures (computed using the Whitehead formula⁹⁵ in R Hmisc⁹⁶; see Table below). Controlling for baseline values of cognitive mechanisms and covariates, an expected sample size of 78 users (33 incomplete + 45 complete) would have 80% power with $\alpha = .05$ to detect a small effect size of a user or environment characteristic on cognitive mechanisms at post ($R^2 = .04 < .10$).

Caregiving Strain			
N=100	Above Mdn	Below Mdn	% sample
Non-user	16	6	22%
User	34	44	78%
% sample	50%	50%	OR=3.4

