7.2 Participant Discontinuation/Withdrawal

Participants are free to withdraw from participation in the study at any time upon request.

A participant's study treatment would be discontinued for the following reasons:

- Significant study intervention non-compliance
- If any clinical adverse event (AE), laboratory abnormality, or other medical condition or situation occurs such that continued participation in the study would not be in the best interest of the participant (see *section 7.3* for dose-limiting toxicities)
- Disease progression which requires discontinuation of the study intervention
- If the participant meets an exclusion criterion (either newly developed or not previously recognized) that precludes further study participation
- Participant unable to receive study intervention.
- Participant decision to withdraw from study treatment and/or the study
- Initiation of prohibited intervention or medication

The reason for participant discontinuation or withdrawal from study treatment will be recorded. Participants who sign the informed consent form but do not receive the

study intervention may be replaced. Participants who sign the informed consent form, and receive the study intervention, and subsequently withdraw, or are withdrawn or discontinued from the study, will be replaced. Participants that withdraw from the study (not only from study treatment, but all study follow-up) will not be contacted for any further study visits.

A participant will be considered lost to follow-up if he or she fails to complete pre-assessment and is unable to be contacted by the study site staff.

The following actions must be taken if a participant fails to complete assessments:

- The site will attempt to contact the participant and counsel the participant on the importance of maintaining the program and ascertain if the participant wishes to and/or should continue in the study.
- Before a participant is deemed lost to follow-up, the investigator or designee will make every effort to regain contact with the participant.
- These contact attempts should be documented in the study file.
- Should the participant continue to be unreachable, he or she will be considered to have withdrawn from the study with a primary reason of lost to follow-up.

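### Is the 80% power that Section 10.2 claims for R² = .04 with 78 users a miscalculation?

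*Combined protocol and SAP*

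**What the plan says.** Section 10.2 sets the enrolment target ("The minimum sample size to achieve is 100", with a ceiling of about 130) and expects 22% non-users, 33% incomplete users and 45% complete users. For the cognitive mechanisms it says that "an expected sample size of 78 users (33 incomplete + 45 complete) would have 80% power" at alpha .05 to detect "a small effect size of a user or environment characteristic on cognitive mechanisms at post". The effect is printed as R² = .04 < .10, and the sentence opens by naming adjustment for the baseline mechanism and the covariates.

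Section 10.3.2 gives the analysis: one regression per characteristic and mechanism, in users only, adjusted for the pre-assessment score of the same mechanism. In addition, "models will control for level of SHUTi engagement and pre-specified covariates". Section 10.3.1 lists the covariates: age, household income, health literacy, and mental and physical health-related quality of life.

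Section 10.2 does not say whether .04 is a partial R² or an increment in R². It gives no variance explained by baseline and covariates, and no formula or software for this calculation. The Whitehead/Hmisc citation belongs to the odds-ratio calculation.

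**The concern.** A common default in power software is a partial R², or the f² derived from it. Put .04 in that way with n = 78 and the power is about 43%, roughly half the claim; 80% would need about 191 users, more than the enrolment ceiling. On that reading the printed figure is simply wrong.

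This is the only power statement for the secondary hypothesis, which covers eight characteristics and two mechanisms. If Aim 2 could detect only effects more than twice the stated size, a null result might be taken as evidence that caregiving context does not matter, and so that tailoring is unnecessary, when the study could not have shown it.

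Two further points add to the doubt. Proximity is recorded in three categories ("Whether bedpartner, live together but not bedpartner, other situation") and would have a larger detectable effect if entered with 2 degrees of freedom. And 78 is every expected user at N = 100, with no allowance in that sentence for a missed post-assessment.

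**Working it through.** **Inputs.** n = 78, alpha .05 and power 80% come from Section 10.2. Model terms come from Sections 10.3.1 and 10.3.2: baseline score (1), covariates (5), engagement level (1) and the tested characteristic (1), so 8 terms and residual df = 78 − 8 − 1 = 69. A two-sided test (1-df F test) is assumed, because the protocol does not state sidedness.

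**Formulas.** Power is the probability that a noncentral F(1, 69; λ) variable exceeds the 5% critical value, 3.98.
- Partial R²: f² = R²/(1 − R²).
- Increment ΔR² over a covariate R² of C: f² = ΔR²/(1 − C − ΔR²).
- Noncentrality: λ = f²·n. A stricter convention uses λ = f²·(u + v + 1), with u = 1 and v = 69, so f²·71.

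**Reproducing the plan's 80%.** Take .04 as an increment and C = .574. Then f² = .04/(1 − .574 − .04) = .04/.386 = .1036, λ = 78 × .1036 = 8.08, and power is 80%. The figure reproduces under this input.

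**Reading .04 as a partial R².** f² = .04/.96 = .0417, λ = 78 × .0417 = 3.25, power 43% (40% under the stricter convention).

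**Detectable effect at 80% power.** f² = .1035, so partial R² = .1035/1.1035 = .094. Under the stricter convention f² = .1137, so partial R² = .1137/1.1137 = .102, and C for an increment of .04 becomes 1 − .04 − .04/.1137 = .608.

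**How power for an increment of .04 depends on C** (λ = f²·n):

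| C | f² | Power |
|---|---|---|
| 0 | .0417 | 43% |
| .30 | .0606 | 57% |
| .50 | .0870 | 73% |
| .57 | .1026 | 80% |
| .60 | .1111 | 83% |
| .65 | .1290 | 88% |
| .70 | .1538 | 93% |

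The unstated input moves power in both directions around 80%. The row C = 0 is hard to credit as an increment, because the model contains the same scale measured at baseline.

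**How exact C must be.** The detectable increment is .094 × (1 − C). It rounds to .04 when it lies between .035 and .045, that is, for C between 1 − .045/.0938 = .52 and 1 − .035/.0938 = .63. If the baseline score alone supplied C, the pre-post correlation would have to be between √.52 = .72 and √.63 = .79. The protocol gives no such correlation, so this is a range to be judged, not a verified value.

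**Convention.** λ = f²·n is the favourable choice. Simulation with random predictors at n = 78 and C = .574 gives about 75%, in line with the stricter convention's need for C of about .61. This is a shift of about 5 points, not a different conclusion.

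**Proximity.** If entered as three categories (2 df, 9 terms, residual df 68), the detectable partial R² is .114 (.124 under the stricter convention), and an increment of .04 needs C of about .65. The protocol lists response options and does not fix the model coding.

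**Missing post-assessments.** At the ceiling, 130 × .78 = 101 users. The loss that still leaves 78 is 1 − 78/101 = 23%. At N = 100 there is no such margin.

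**The case for a change.** The best case for a change is that a power claim resting on one unwritten number cannot be checked. Naming an adjustment is not the same as giving its strength, and at C = .30 the power is 57%. A reader who takes .04 as a partial R² is misled by a factor of more than two, and one or two sentences would prevent that.

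The uncheckability stands: the label and the covariate R² should ideally have been printed. The claim of error does not. The sentence starts from adjustment for baseline, which points to an increment, and a covariate R² anywhere from about .52 to .63 returns the printed .04. No figure in the protocol contradicts this.

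The subsidiary points are weaker. The .10 beside .04 reads more naturally as the benchmark for calling an effect small than as a promised bound for every predictor, so the 2-df value for proximity does not breach it. Post-assessment loss is partly covered by enrolment up to about 130 and by the rule in Section 7.2 that participants who receive the intervention and "subsequently withdraw, or are withdrawn or discontinued from the study, will be replaced", though the power sentence relies on neither. A blunt replacement stating 80% power for a partial R² of .09 would carry its own defect, since simulation with random predictors puts that nearer 75%.

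**Conclusion.** This is missing detail, not a mistake in the plan. With 78 users and a 1-df predictor, 80% power corresponds to a partial R² of about .09 to .10, or equally to an R² increment of .04 when baseline and covariates explain about 57 to 61% of the post-score variance. The printed claim is right under the second description, which is the natural one for this model, and that description rests on an assumption the documents neither state nor exclude.

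Nothing in the conduct or analysis depends on resolving it. The minimum of 100 is supported by the primary odds-ratio calculation, the Aim 2 models are specified independently of the power sentence, and Aim 2 is a secondary aim of a single-arm pilot. Once data are in, the estimated effects and their intervals will show what Aim 2 could and could not exclude. A reader interpreting a null result should keep the partial R² of .09 to .10 in mind, and a somewhat larger value (.114 to .124) for proximity if it is entered as three categories. These figures assume a two-sided test, the 8-term model (9 terms for three-category proximity) and 78 users with post-assessment data.
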